#### **8.5. Patient Profiles**

Listing for patient profiles will be produced at only Final Analyses if at least one event is reported below.

CV event (

- Arrhythmias,
- Congestive Heart Failure,
- Cerebrovascular Events/Stroke and Transient Ischemic Attack,
- Deep Vein Thrombosis (DVT)/ Pulmonary Embolism (PE),
- Myocardial Infarction (MI)/ Unstable Angina (UA),

CONFIDENTIAL

207660

Peripheral Arterial Thromboembolism,  
Pulmonary Hypertension,  
Revascularization,  
Valvulopathy)  
And Death.

## 8.6. Exposure

The number and percentage of participants treated will be presented by the number of injection.

- Blind Phase

The dosage will be summarized by muscle region below, Joint and total. The dosage will be listed by muscle region, joint and total.

Joint	Each muscle region
Elbow	Biceps brachii
	Brachialis
	Brachioradialis
Wrist	Flexor carpi radialis
	Flexor carpi ulnaris
Finger	Flexor digitorum profundus
	Flexor digitorum superficialis
Thumb	Flexor pollicis longus
	Adductor pollicis

- Open Label Phase

The dosage will be summarized by treatment phase (2nd, 3rd and 4th treatment), muscle region below, Joint and total. The dosage will be listed by treatment phase and muscle region, Joint and total.

Joint	Each muscle region
Elbow	Biceps brachii
	Brachialis
	Brachioradialis
Wrist	Flexor carpi radialis
	Flexor carpi ulnaris
Finger	Flexor digitorum profundus
	Flexor digitorum superficialis
	Lumbricales interossei
Thumb	Flexor pollicis longus

## CONFIDENTIAL

207660

Joint	Each muscle region
	Adductor pollicis
	Opponens
Forearms	Pronator teres
	Pronator quadratus
Shoulder	Teres major
	Latissimus dorsi
	Pectoralis major
	Subscapularis

CONFIDENTIAL

207660

**10. APPENDICES**

**10.1. Appendix 1: Protocol Deviation Management and Definitions  
for Per Protocol Population**

Per Protocol Population is not defined in this study.

CONFIDENTIAL

207660

**10.2. Appendix 2: Schedule of Activities**

**10.2.1. Protocol Defined Schedule of Events**

	Screening a	Blind phase 1) If a participant meets the eligibility at V5/ QRV, the participant will move forward to the open- label phase						Open-label phase If a participant meets the eligibility at V5/QRV, the participant will move forward to the next treatment phase						Completion visit
		Part 1					Eligibility evaluation b	Part 2/Part 3/ Part 4				Eligibility evaluation b		
Visit	SV	V1 (Day 1)	V2	V3	V4	V5 c (Eligibility evaluation)	QRV	V1	V2	V3	V4	V5 d (Eligibility evaluation)	QRV	Final Visit
Time from initial injection (Day 1) (Weeks)	—	0	2	4	6	12	Allowable Week 16 to 36 e	—	—	—	—	—	Allowable Week 24 to 36 e	48/ Withdrawal
Time from injection day in each treatment phase (Weeks)	—	0	2	4	6	12	16/ 20/ 24/ 28/ 32/ 36	0	2	4	6	12	16/ 20/ 24	-
Acceptable visit windows (days)		—	±4	±4	±4	+4 f	±14 g	(+4) v	±4	±4	±4	+4 f	±14 g	±4
Written informed consent	X h													
Randomization		X i												
Injections		X						X						
Evaluation of eligibility						X	X					X	X	
Inclusion/exclusion criteria j	X	X i												
Participant demography	X													
MAS k	X	X i	X	X	X	X	X	X i,t	X	X	X	X	X	X
NRS l		X i	X	X	X	X		X i,t	X	X	X	X		(X) r
DAS		X i	X	X	X	X		X i,t	X	X	X	X		(X) r
CGI by a investigator			X	X	X	X			X	X	X	X		(X) r
CGI by a patient			X	X	X	X			X	X	X	X		(X) r
Time to patient-reported onset of spasticity symptom relief			X						X					
Patient-reported benefit of injection				X	X	X				X	X	X		(X) r
Physical examination	X													

CONFIDENTIAL

207660

	Screening a	Blind phase 1) If a participant meets the eligibility at V5/ QRV, the participant will move forward to the open- label phase					Eligibility evaluation b	Open-label phase If a participant meets the eligibility at V5/QRV, the participant will move forward to the next treatment phase					Completion visit	
		Part 1						Part 2/Part 3/ Part 4						Eligibility evaluation b
Visit	SV	V1 (Day 1)	V2	V3	V4	V5 c (Eligibility evaluation)	QRV	V1	V2	V3	V4	V5 d (Eligibility evaluation)	QRV	Final Visit
(complete version)														
Physical examination (simplified version)		X 				X		X 1,t				X		X
Medical history	X	X 												
Vital signs m	X	X 				X		X 1,t				X		X
Height	X													
Body weight	X					X u	X u					X u	X u	
Pulmonary function test	X	X				X	X u					X	X u	X
Electrocardiogram	X					X u	X u					X u	X u	
Pregnancy test n	X	X 				X u	X u					X s, u	X u	X
Laboratory test o	X					X						X		X
Adverse events p	X	X	X	X	X	X	X	X	X	X	X	X	X	X
Concomitant medications/therapies	X	X 	X	X	X	X	X	X	X	X	X	X	X	X
Testing for neutralising antibodies q	X					X								X

- Test items for screening must be performed from 4 weeks to 1 weeks before Day 1 visit (±3 days).
- Eligibility evaluation (Qualification for Retreatment Visit: QRV) will be performed at V5 as a starting point if a participant does not meet the criteria only. The evaluation is performed at a 4-week interval, V5 as a starting point, The QRV when a participant meets the criteria will be a same day as the injection in the next treatment period.
- If a participant is evaluated to meet the eligibility for the injection in the blind phase at V5, the participant will move forward to Part 2 in the open-label phase (Namely, V5 in Part 1 and V1 in Part 2 is a same day). If the participant does not meet the eligibility, QRV will be performed 4 weeks later, at V5 as a starting point.
- If a participant is evaluated to meet the eligibility at V5 in the open-label phase, the participant will move forward to the next treatment phase (V5 and V1 in the next treatment phase is a same day). If the participant does not meet the eligibility, QRV is performed 4 weeks later, V5 as a starting point. If V5 in each treatment phase is at Week 48 after initial injection, V5 will be considered to be completion visit (FV). However, for the testing items, pre-scheduled tests at

## CONFIDENTIAL

207660

V5 and neutralizing antibody tests will be performed. If V5 in Parts 2 and 3 is performed at Week 36 or later, after completion of V5, completion visit will be performed at Week 48.

- e. QRV is allowable to perform from initial injection to Week 36. Eligibility evaluation (QRV) will not be performed after Week 36.
- f. V5 must be performed at least 84 days after V1.
- g. The acceptable visit windows will be -14 to +4 days if QRV is performed at Week 36.
- h. Must be performed earlier than any other procedures
- i. Must be performed before injection of the product
- j. For inclusion/exclusion criteria, the items to be observed are different between screening phase and Day 1. For details, refer to Protocol Section 6.1 and Section 6.2.
- k. For MAS evaluation, the items to be evaluated differ depending on the treatment phase. For details, refer to Protocol Section 9.1.1.1.
- l. MAS evaluation will be followed by NRS evaluation. For NRS evaluation, items to be evaluated differ. For details, refer to Protocol Section 9.1.1.2.
- m. Body temperature, heart rate, and blood pressure will be measured as vital signs.
- n. Women of childbearing potential will be only performed. Serum hCG pregnancy test must be performed at screening, and urine hCG pregnancy test after randomization. The tests can be performed beyond the protocol specifications if an investigator considers to be necessary.
- o. For laboratory test items, refer to Protocol Section 12.2. Attachment 2. Fasting is not required for blood collection.
- p. Adverse events and serious adverse events collection period will be from the initial injection day (Day 1) to completion visit (FV).
- q. Neutralizing antibody testing is performed 3 times in each participant. The first test will be performed in screening phase, the second is at V5 in the blind phase, and the third is at completion visit.
- r. A participant who withdraws the study before 12 weeks after last injection will be performed.
- s. Perform if V5 in each treatment phase is at Week 48 after initial injection
- t. Not necessary to perform doubly as V1 assessment if the same assessment is performed at V5 or QRV. If V1 assessment or retreatment cannot be performed on the same day as V5 or QRV, MAS assessment should be performed again on the day of visit for the V1 assessment.
- u. Evaluation of retreatment is performed only when the dosing conditions (1 to 5) of retreatment evaluation are met. If V1 assessment or retreatment cannot be performed on the same day as V5 or QRV, body weight, pulmonary function test, electrocardiogram, and pregnancy test should not be performed again on the day of visit for V1 assessment.
- v. V1 assessment in Part 2 or subsequent parts should be performed as a rule on the same day as V5 or QRS (when eligibility was confirmed) of the previous part. If this is not possible, the V1 assessment may be performed on another day but within the acceptable visit window.

CONFIDENTIAL

207660

**10.3. Appendix 3: Assessment Windows****10.3.1. Definitions of Assessment Windows for Efficacy Analyses (only Final Visit and Withdraw Visit, and only Final Analyses)**

If the Visit 5 in last treatment cycle coincides with Final Visit (e.g., Visit 5 in 3rd treatment cycle is achieved on Week 48 from the initial dose), the efficacy data will be entered as Final Visit, not the last visit in the treatment cycle. However, actually the data at the last visit is not missing. Therefore, in the following cases, the Final Visit data will be treated as the Visit 5 in the last treatment cycle for the efficacy analyses.

Where the participant (except for the withdrawn from study) who was qualified for re-treatment:

- At Week 12 in Blind Phase, 2nd and 3rd Open Label Phase
- At Week 12 in Blind Phase and at Week 24 in 2nd Open Label Phase.
- At Week 16 in Blind Phase and at Week 20 in 2nd Open Label Phase.
- At Week 20 in Blind Phase and at Week 16 in 2nd Open Label Phase.
- At Week 24 in Blind Phase and at Week 12 in 2nd Open Label Phase.
- At Week 36 in Blind Phase.

CONFIDENTIAL

207660

## 10.4. Appendix 4: Study Phases and Treatment Emergent Adverse Events

### 10.4.1. Study Phases for Concomitant Medication

Study Phase	Definition
Prior	"Taken prior to study?" is marked "Yes" on eCRF OR Medication Start Date < First Study Treatment Date OR Medication Start Date is missing.
Concomitant	"Ongoing medication?" is marked "Yes" or missing on eCRF OR Medication End Date ≥ First Study Treatment Date OR Medication End Date is missing

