#### NOTES:

- Please refer to [Appendix 7: Reporting Standards for Missing Data](#) for handling of missing and partial dates for concomitant medication. Use the rules in this table if concomitant medication date is completely missing.

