### 10.4.2. Study Phases for Adverse Events

Flag	Definition
Treatment Emergent	
 
First Study Treatment Date ≤ AE Start Date ≤ Final Visit Date/Early Withdrawal Date
 

Blind phase (until second dose)	
 
First Study Treatment Date ≤ AE Start Date ≤ Second Study Treatment Date AND AE Start Time < Second Study Treatment Time IF AE Start Time is collected
 
First Study Treatment Date ≤ AE Start Date < Second Study Treatment Date IF AE Start Time is not collect.
 

Blind phase (within 84 days)	
 
First Study Treatment Date ≤ AE Start Date ≤ First Study Treatment Date + 83 days
 

Open-Label Phase (2nd Treatment)	
 
Second Study Treatment Date ≤ AE Start Date ≤ Third Study Treatment Date AND Second Study Treatment Time ≤ AE Start Time < Third Study Treatment Time IF AE Start Time is collected
 
Second Study Treatment Date ≤ AE Start Date < Third Study Treatment Date IF AE Start Time is not collected
 

Open-Label Phase (3rd Treatment)	
 
Third Study Treatment Date ≤ AE Start Date ≤ Fourth Study Treatment Date AND Third Study Time ≤ AE Start Time < Fourth Study Treatment Time IF AE Start Time is collected
 
Third Study Treatment Date ≤ AE Start Date < Fourth Study Treatment Date IF AE Start Time is not collected
 

Open-Label Phase (4th Treatment)	
 
Fourth Study Treatment Date ≤ AE Start Date ≤ Final Visit Date AND Fourth Study Time ≤ AE Start Time IF AE Start Time is collected
 
Fourth Study Treatment Date ≤ AE Start Date ≤ Final Visit Date IF AE Start Time is not collected
 

Drug related	
 
If relationship to Study treatment(GSK1358820/Placebo) is marked 'YES' on CRF OR value is missing.
 

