**10.7.2.1. Handling of Missing and Partial Dates**

Element	Reporting Detail
General	
 
• Partial dates will be displayed as captured in participant listing displays.
 

Concomitant Medications and Surgery	
 
• Partial dates for any concomitant medications recorded in the CRF will be imputed using the following convention: 
 
○ If the partial date is a start date, a '01' will be used for the day and 'Jan' will be used for the month
 
○ If the partial date is a stop date, a '28/29/30/31' will be used for the day (dependent on the month and year) and 'Dec' will be used for the month.
 
 
 
• The recorded partial date will be displayed in listings.
 

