**10.12.4.2. Final Analyses**

Study Population Tables					
No.	Population	IDSL / Example Shell	Title	Programming Notes	Deliverable
Participant Disposition					
1.15.	ITT1	ES1	Summary of Participant Disposition for the Participant Conclusion Record	ICH E3, FDAAA, EudraCT Include total arm (240 U + 400 U)	SAC
Protocol Deviation					
1.16.	ITT1	DV1	Summary of Important Protocol Deviations	ICH E3 Include total arm (240 U + 400 U)	SAC
Population Analysed					
1.17.	Screened	SP1	Summary of Study Populations	IDSL	SAC
Prior and Concomitant Medications					
1.18.	ITT1	CM1	Summary of Prior Medications	Include total arm (240 U + 400 U)	SAC
1.19.	ITT1	CM1	Summary of Concomitant Medications	ICH E3 Include total arm (240 U + 400 U)	SAC
1.20.	ITT1	POP_T2	Summary of Rehabilitation	Include total arm (240 U + 400 U)	SAC
Actual dose					
1.21.	ITT1	SAFE_T4	Summary of Actual Dosage in Exposed Muscle Region by Treatment Cycle and Muscle Region.		SAC
1.22.	ITT1	SAFE_T4	Summary of Actual Dosage in Exposed Joint by Treatment Cycle and Joint		SAC

CONFIDENTIAL

207660

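### Concomitant medication has no end at retreatment and a blank 'Ongoing' field overrides a recorded pre-dose stop date, which limits what the by-arm tables show about co-medication in the blinded comparison

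*SAP*

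**What the plan says.** Section numbers here are those of the amended plan (August 2018).

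Section 10.4.1 is titled as a definition of study phases for medication but defines only two categories, Prior and Concomitant. They may overlap, and the conditions within each are joined by OR.

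- **Concomitant:** the field 'Ongoing medication?' "is marked 'Yes' or missing on eCRF", or "Medication End Date ≥ First Study Treatment Date", or "Medication End Date is missing".
- **Prior:** 'Taken prior to study?' is Yes, or the start date precedes the first treatment, or "Medication Start Date is missing".

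The note below the table refers partial dates to Appendix 7 and adds: "Use the rules in this table if concomitant medication date is completely missing". Section 10.7.2.1 imputes partial start dates early: "If the partial date is a start date, a '01' will be used for the day and 'Jan' will be used for the month". Partial stop dates are imputed late.

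The only by-arm displays of concomitant drugs are Table 1.11 (interim) and Table 1.19 (final), each titled "Summary of Concomitant Medications", on ITT1, with no phase restriction. Section 3.1 limits interim medication data to drugs started on or before the Week 24 visit.

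**The concern.** The randomised contrast lasts only until the second treatment. After that, both arms receive 400 units in total (Section 2.3). Retreatment is possible from day 84 (Section 10.2.1, footnote f). A drug first taken after retreatment is nevertheless tabulated under the original arm, beside drugs taken while the arms still differed.

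The plan applies a blinded window elsewhere. Adverse events have two blind-phase flags and one per later cycle (Section 10.4.2). Rehabilitation is presented for the Blind Phase (Section 6.6). Secondary efficacy stops at Week 12 because of retreatment (Section 7.2.3). Medication is the co-treatment left without such a window.

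Separately, the OR logic lets an empty field outrank a recorded date, so drugs stopped before the first injection can enter the concomitant tables. What is at stake is how well a reader can judge from the tables whether co-medication was balanced up to Week 6 or Week 12. The interim report is the one made for regulatory submission (Section 3.1), so Table 1.11 will be read for this purpose.

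**Working it through.** The SAP gives no figure to reproduce. The check is to apply the rule as written and then do the calendar arithmetic.

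**1. The concomitant rule.** Count days from first treatment (day 0) and suppose retreatment on day 84. Cross the three possible answers to 'Ongoing' with four kinds of stop date:

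| 'Ongoing' | Stop day −10 | Stop day +30 | Stop day +100 | Stop blank |
|---|---|---|---|---|
| Yes | concomitant | concomitant | concomitant | concomitant |
| No | not concomitant | concomitant | concomitant | concomitant |
| blank | **concomitant** | concomitant | concomitant | concomitant |

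Eleven of the 12 cells are concomitant. The blank/day −10 cell is the misclassification: the recorded stop date settles the matter, yet the empty field decides. Under the superseded rule of April 2018 (Section 9.4.1 of that plan) a recorded pre-dose stop date made the drug prior, so the override came with the amendment.

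**2. No end at retreatment.** A drug used on days +20 to +30 and one started on day +100, after retreatment on day 84, receive the same flag. Nothing in the rule refers to the second treatment.

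**3. The prior rule.** A drug marked No for 'Taken prior to study?' becomes Prior if its start date is blank, or if a partial start date is imputed to before dosing. Because the categories overlap, it is still concomitant if it is ongoing, ends on or after first treatment, or has no stop date. This inflates the prior table. It does not remove the drug from Tables 1.11 or 1.19.

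**4. Share of each table's window after retreatment.** Share = (end of window − retreatment week) / end of window. The final window is 48 weeks. The interim cut follows Section 3.1, which for retreatment at Week 16 uses the open-label Week 12 visit, nominally 16 + 12 = Week 28.

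| Retreated at | Interim cut | Interim share | Final share |
|---|---|---|---|
| Week 12 | 24 | 12/24 = 50% | 36/48 = 75% |
| Week 16 | 28 | 12/28 = 43% | 32/48 = 67% |
| Week 20 | 24 | 4/24 = 17% | 28/48 = 58% |
| Week 24 | 24 | 0% | 24/48 = 50% |
| Week 36 | 24 | 0% | 12/48 = 25% |

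These are shares of calendar time, not of drugs. Drugs continuing from baseline also enter the tables, and the SAP gives no rate of new starts.

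**The case against.** The strongest reply is that nothing is contradicted. Section 6.5 promises a descriptive summary of all prior and concomitant medication, and the tables deliver it. No estimate or interval uses the flag. Treating unknown dates as concomitant is a usual conservative convention, and the note on completely missing dates suggests that the blank-field conditions were meant for records without dates. That is a fair guess at the intent, but the written rule sets no precedence, and a programmer following it would flag the blank/day −10 record.

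Three further points stand:

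- Medication listings exist at interim (Listing 11) and final (Listing 42), and Section 10.5.2 says listings show time relative to dosing. With 120 participants planned, a manual split may be feasible.
- The blank-field problem needs incomplete records to survive database cleaning, and its frequency is not known.
- Whether drugs affecting muscle tone are restricted in the Blind Phase is a protocol matter. If they are, important breaches would appear by arm in the deviation tables (1.04 and 1.16).

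A reader might infer more: that balance cannot be assessed at all, that the Week 6 comparison is biased, or that newly started drugs disappear from the concomitant tables. The documents support none of these. The listings remain, the primary analysis does not use medication flags, and a new drug misfiled as prior normally stays concomitant as well.

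**Conclusion.** The point holds as a limited one. Section 10.4.1 misclassifies a drug with a recorded pre-dose stop date and a blank ongoing field, and it gives concomitant medication no end at retreatment. Tables 1.11 and 1.19 therefore mix medication from the randomised comparison with medication from the open-label period, and can include drugs stopped before dosing.

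The missing end at retreatment matters more and does not depend on blank fields. For a participant retreated at the earliest visit, half of the interim window and three quarters of the final one lie outside the randomised contrast. For one retreated at Week 24 or later, the interim share is zero. The resulting effect on any by-arm percentage cannot be calculated from the SAP, which gives neither retreatment timing, nor medication rates, nor the rate of blank fields.

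The consequence is confined to interpreting co-medication balance. The primary estimate is unaffected, and rehabilitation is already covered for the Blind Phase. This is a worthwhile improvement rather than a serious fault.

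**What to change.** **1. Add a precedence rule to Section 10.4.1.** A complete recorded date decides the category. Blank fields and imputed dates are used only when no complete date is recorded. It follows that:

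- a complete stop date before first treatment makes the drug prior and never concomitant;
- a complete start date before first treatment always makes the drug prior, so one started between screening and Day 1 and stopped before dosing is not left in neither category;
- 'Taken prior to study?' = No overrides only a missing or imputed start date, never a complete date.

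**2. Add a blind-phase concomitant flag.** It covers use on or after first treatment, with a start before second treatment, or up to Final Visit or Early Withdrawal if there is no second treatment. This matches the blind-phase adverse-event flag in Section 10.4.2. Add one by-arm table on this flag and keep Tables 1.11 and 1.19 as whole-period summaries.

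The cost is SAP wording, one derived flag and one extra table. No new data are needed.

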#### NOTES:

- Please refer to [Appendix 7: Reporting Standards for Missing Data](#) for handling of missing and partial dates for concomitant medication. Use the rules in this table if concomitant medication date is completely missing.

### 10.4.2. Study Phases for Adverse Events

Flag	Definition
Treatment Emergent	
 
First Study Treatment Date ≤ AE Start Date ≤ Final Visit Date/Early Withdrawal Date
 

Blind phase (until second dose)	
 
First Study Treatment Date ≤ AE Start Date ≤ Second Study Treatment Date AND AE Start Time < Second Study Treatment Time IF AE Start Time is collected
 
First Study Treatment Date ≤ AE Start Date < Second Study Treatment Date IF AE Start Time is not collect.
 

Blind phase (within 84 days)	
 
First Study Treatment Date ≤ AE Start Date ≤ First Study Treatment Date + 83 days
 

Open-Label Phase (2nd Treatment)	
 
Second Study Treatment Date ≤ AE Start Date ≤ Third Study Treatment Date AND Second Study Treatment Time ≤ AE Start Time < Third Study Treatment Time IF AE Start Time is collected
 
Second Study Treatment Date ≤ AE Start Date < Third Study Treatment Date IF AE Start Time is not collected
 

Open-Label Phase (3rd Treatment)	
 
Third Study Treatment Date ≤ AE Start Date ≤ Fourth Study Treatment Date AND Third Study Time ≤ AE Start Time < Fourth Study Treatment Time IF AE Start Time is collected
 
Third Study Treatment Date ≤ AE Start Date < Fourth Study Treatment Date IF AE Start Time is not collected
 

Open-Label Phase (4th Treatment)	
 
Fourth Study Treatment Date ≤ AE Start Date ≤ Final Visit Date AND Fourth Study Time ≤ AE Start Time IF AE Start Time is collected
 
Fourth Study Treatment Date ≤ AE Start Date ≤ Final Visit Date IF AE Start Time is not collected
 

Drug related	
 
If relationship to Study treatment(GSK1358820/Placebo) is marked 'YES' on CRF OR value is missing.
 

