### 8.1. Adverse Events Analyses

Adverse events analyses including the analysis of adverse events (AEs), Serious (SAEs) and other significant AEs will be based on GSK Core Data Standards. The details of the planned displays are provided in [Appendix 12: List of Data Displays](#).

Adverse events that occurred in the overall study period, blinded period and open-label period will be summarized for each treatment group. The treatment group is based on dose actually given in blind period. For the blinded period, 2 patterns of analyses on adverse events will be performed, one is on adverse events that occurred between the initial dose and the first dose in the open-label period (or at the completion of study if no dose is given in the open-label period or at the study withdrawal), and another one is on adverse events that occurred within 84 days from the initial dose.

Overall study period (Treatment Emergent AEs)

Blind phase

1. AEs occurred between the initial dose and the first dose in the open-label period (or at the completion of study if no dose is given in the open-label period or at the study withdrawal)
2. AEs occurred within 84 days from the initial dose

Open-label phase

- 3.01. AEs occurred during 2nd treatment cycle.
- 3.02. AEs occurred during 3rd treatment cycle.
- 3.03. AEs occurred during 4th treatment cycle.

The number and percentages of participants who experience at least one AE will be presented for each category of AE listed as below by treatment group.

- All Treatment Emergent AEs (by SOC and PT, by SOC, PT and Maximum Intensity)
- Common AEs ( $\geq 3\%$ ) (by overall frequency)
- Drug Related AEs (by SOC and PT, by SOC, PT and Maximum Intensity)
- Non-Fatal Serious AEs
- Drug Related Non-Fatal Serious AEs
- AEs Leading to Withdrawal from Study (by SOC and PT)
- Most Common Serious Drug Related AEs (by overall frequency)
- Most Common Non-Serious Drug Related AEs (by overall frequency)
- Common ( $\geq 5\%$ ) Non-Serious AEs (by SOC and PT)
  - Number of Participant and Occurrences will be presented.

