3.116.	Safety 2	AE1	Summary of Adverse Events Leading to Withdrawal from Study by System Organ Class and Preferred Term in Open Label Phase (2nd Treatment)	Open Label Phase (2nd Treatment) See the Section 10.4.2 . Three treatment arms (240, 400 and 240 + 400U)	SAC
3.117.	Safety 3	AE1	Summary of Adverse Events Leading to Withdrawal from Study by System Organ Class and Preferred Term in Open Label Phase (3rd Treatment)	Open Label Phase (3rd Treatment) See the Section 10.4.2 . Three treatment arms (240, 400 and 240 + 400U)	SAC

CONFIDENTIAL

207660

Safety: Tables					
No.	Population	IDSL / Example Shell	Title	Programming Notes	Deliverable
3.118.	Safety 4	AE1	Summary of Adverse Events Leading to Withdrawal from Study by System Organ Class and Preferred Term in Open Label Phase (4th Treatment)	Open Label Phase (4th Treatment) See the Section 10.4.2. Three treatment arms (240, 400 and 240 + 400U)	SAC
Laboratory: Chemistry					
3.119.	Safety 1	LB1	Summary of Chemistry by Visit	Summarize data at Screening Visit, in Blind Phase and at Final Visit.	SAC
3.120.	Safety 1	LB1	Summary of Chemistry Changes from Baseline by Visit	Summarize data in Blind Phase and at Final Visit. ICH E3	SAC
3.121.	Safety 1	LB3	Summary of Chemistry Shifts from Baseline Relative to Normal Range		SAC
3.122.	Safety 1	LB15	Summary of Worst Case Chemistry Results Relative to Normal Range Post-Baseline Relative to Baseline	ICH E3	SAC
Laboratory: Hematology					
3.123.	Safety 1	LB1	Summary of Hematology by Visit	Summarize data at Screening Visit, in Blind Phase and at Final Visit.	SAC
3.124.	Safety 1	LB1	Summary of Hematology Changes from Baseline	Summarize data in Blind Phase and at Final Visit. ICH E3	SAC
3.125.	Safety 1	LB3	Summary of Hematology Shifts from Baseline Relative to Normal Range		SAC
3.126.	Safety 1	LB15	Summary of Worst Case Hematology Results Relative to Normal Range Post-Baseline Relative to Baseline	ICH E3	SAC

CONFIDENTIAL

207660

Safety: Tables					
No.	Population	IDSL / Example Shell	Title	Programming Notes	Deliverable
Laboratory: Urinalysis					
3.127.	Safety 1	UR1	Summary of Worst Case Urinalysis Results (Discrete or Character Values) Post-Baseline Relative to Baseline	ICH E3	SAC
Laboratory: Hepatobiliary (Liver)					
3.128.	Safety 1	LIVER1	Summary of Liver Monitoring/Stopping Event Reporting	This display will be presented if liver events occur.	SAC

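### Adverse-event cycle flags in section 10.4.2 have no end date for a participant's last cycle when fewer than four injections are given, so by-cycle incidence is biased downward

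*SAP*

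**What the plan says.** All references are to the amended SAP. Section 10.4.2 defines the flags that place each adverse event in a study period:

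- Blind phase (until second dose): "First Study Treatment Date ≤ AE Start Date ≤ Second Study Treatment Date"
- 2nd treatment: "Second Study Treatment Date ≤ AE Start Date ≤ Third Study Treatment Date"
- 3rd treatment: "Third Study Treatment Date ≤ AE Start Date ≤ Fourth Study Treatment Date"
- 4th treatment: "Fourth Study Treatment Date ≤ AE Start Date ≤ Final Visit Date"
- Treatment emergent: "First Study Treatment Date ≤ AE Start Date ≤ Final Visit Date/Early Withdrawal Date"

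Each of the first four rows has a version for when the event's start time is collected and one for when it is not. Neither version names an alternative end for the first three rows. A separate blind-phase flag runs for a fixed 84 days from the first injection and needs no later injection.

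Section 8.1 describes the blind phase as running from the initial dose to the first open-label dose, "or at the completion of study if no dose is given in the open-label period or at the study withdrawal". For the open-label period it lists the second, third and fourth cycles without saying when each ends.

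The schedule in section 10.2.1 requires V5 to fall at least 84 days after V1, and its footnote e states: "Eligibility evaluation (QRV) will not be performed after Week 36".

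**The concern.** A participant's last cycle has, by definition, no following injection. If that cycle is the first, second or third, the flag compares the event's start date with a date that does not exist. The SAP specifies SAS (section 10.5.1), where a date is never less than or equal to a missing value. The condition fails and the event gets no cycle flag.

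The Safety 1, 2 and 3 populations in section 4 depend on the number of treatments received, so the same participant stays in the denominator. Numerators can only shrink. The loss falls on participants who withdrew or were not injected again.

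Safety and tolerability of 400 units is a secondary objective, and section 8.2 promises events of special interest by treatment cycle. The final tables exposed include:

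- all adverse events: 3.62, 3.64, 3.65
- events of special interest: 3.95, 3.97, 3.98
- non-fatal serious events: 3.101, 3.103, 3.104
- events leading to withdrawal, where the event begins in the cycle of withdrawal: 3.114, 3.116, 3.117

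**Working it through.** **1. The rows side by side.** The treatment-emergent row ends at the Final Visit or Early Withdrawal Date. The 4th-treatment row ends at the Final Visit only. The other three end only at the next injection. Section 8.1 supplies completion or withdrawal as the end of the blind phase, so 10.4.2 contradicts it there. No section supplies an end for cycles 2 and 3.

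**2. Which schedules are exposed.** Inputs, from sections 2.3 and 10.2.1: at most 1 + 3 = 4 injections; earliest re-injection at Week 12 of a cycle, then every 4 weeks; none after Week 36. In nominal weeks this allows 19 schedules: 1 with one injection, 7 with two, 10 with three and 1 with four. Three minimum cycles take 3 × 84 = 252 days = 36 weeks, so only 0/12/24/36 reaches a fourth injection. As a check, the enumeration returns exactly the six schedules that section 10.3.1 lists as having their last V5 at Week 48. In 18 of 19 schedules the last cycle has no end date. This counts schedules, not participants.

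**3. The flags applied literally.** Date-only version; a comparison with a missing date counts as not met.

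| Participant | Event day | Cycle flag | 84-day flag |
|---|---|---|---|
| 1 injection, withdrawn day 60 | 50 | none | yes |
| 1 injection, withdrawn day 120 | 100 | none | no |
| 2 injections, withdrawn day 150 | 140 | none | no |
| 2 injections, completer | 200 | none | no |
| 3 injections (Weeks 0/12/28), completer | 250 | none | no |
| 3 injections, withdrawn day 260 | 100 | cycle 2 | no |
| 4 injections, completer | 300 | cycle 4 | no |
| 4 injections, withdrawn day 310, no Final Visit date | 300 | none | no |
| 4 injections, withdrawn day 310, withdrawal visit taken as Final Visit | 300 | cycle 4 | no |

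All nine events are treatment emergent. Five get neither a cycle flag nor the 84-day flag, and a sixth gets the 84-day flag only. With every window ending at the next injection or, failing that, at the Final Visit or Early Withdrawal Date, each of the nine falls in exactly one cycle.

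**4. Share of participants affected.** The SAP gives no retreatment rates, so this rests on an assumption. Let q be the probability of qualifying at each V5, and ignore dropout. A fourth injection needs three qualifications in a row, so the share whose last cycle is 1, 2 or 3 is 1 − q³:

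- q = 0.5: 1 − 0.125 = 0.875 (88%)
- q = 0.7: 1 − 0.343 = 0.657 (66%)
- q = 0.9: 1 − 0.729 = 0.271 (27%)

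**5. Interim analysis (section 3.1).** A participant re-treated at Week 20 is cut at open-label Week 4, nominally 20 + 4 = Week 24. A third injection could not come before 20 + 12 = Week 32, so the third date cannot exist. A participant re-treated at Week 12 or 16 is cut at open-label Week 12 and lacks a third date unless re-injected on that cut-off visit.

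**The case against.** The strongest reply is that nothing disappears from the report. Overall-period tables (for example 3.61, 3.94, 3.100, 3.113) use the treatment-emergent flag. The fixed-window tables (for example 3.63, 3.96, 3.102, 3.115) give a complete 84-day comparison of the randomised groups. Listings 53, 56, 57 and 59 keep every event. For the blind phase section 8.1 already states an end, so that part is a contradiction to reconcile, not a missing rule. A programmer might also repair the flags unprompted. All of this stands, and it limits the damage to the until-second-dose and cycle tables. It does not rescue those tables: the 84-day flag covers only cycle 1, overall-period tables cannot give by-cycle rates, and a silent repair would leave the end date unspecified in the plan.

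Two stronger readings are tempting but unsupported.

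- A reader might infer that every event leading to withdrawal is lost, so that Tables 3.114, 3.116 and 3.117 must be empty. The flags use the event's start date, so an event that began before a later injection keeps its earlier cycle flag. Withdrawal events starting in the first 84 days reach Table 3.115. A withdrawal in cycle 4 may be captured, because the schedule places the Final Visit at Week 48 or withdrawal.
- A reader might infer that most participants are affected. With no retreatment rates in the document this cannot be established: under the assumption above it requires q below 0.794. Completers with four injections are unaffected.

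**Conclusion.** The concern holds for the by-cycle displays. As written, section 10.4.2 gives wrong numerators, always in the downward direction, for the until-second-dose and cycle 2 and 3 tables. It leaves cycle 4 withdrawals dependent on whether the withdrawal visit counts as the Final Visit, and it conflicts with section 8.1 on the blind phase. The size depends on how often participants qualify for re-injection: 27% to 88% of participants have an exposed last cycle for q between 0.9 and 0.5, with q assumed constant and dropout ignored. At the interim, the loss from the cycle 2 tables is certain only for those re-treated at Week 20; for Week 12 and Week 16 re-treatment it depends on re-injection at the cut-off visit.

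**What to change.** In section 10.4.2:

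- End the blind-phase (until second dose), 2nd- and 3rd-treatment windows at the next treatment date or, if there is none, at the Final Visit/Early Withdrawal Date. For the interim, use the data cut-off date where no next treatment has occurred.
- End the 4th-treatment window at the Final Visit/Early Withdrawal Date, matching the treatment-emergent row.
- Align the blind-phase row with section 8.1, and state in 8.1 the same end rule for the open-label cycles.

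The cost is one line per flag in the SAP and in the derivation program. No new data are needed.
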